The study is a prospective, randomized, multi-center trial designed to demonstrate the safety and efficacy of the C-Pulse[®] System in relieving heart failure symptoms in patients with ACC/AHA Stage C, NYHA Class III to ambulatory Class IV heart failure. Reduction in heart failure symptoms will be demonstrated by increased freedom from heart failure related hospitalization or death in subjects implanted and treated with the C-Pulse System as compared to a concurrent, randomized control group receiving standard optimal medical therapy (OMT).

Patients will be enrolled into the trial upon providing informed consent. Procedures related directly to the study must not be performed prior to informed consent. Following confirmation of subject eligibility, subjects will be randomized to one of two treatment arms, Treatment or Control, in a 1:1 allocation utilizing a random permuted block design stratified by study center. The Treatment group subjects will receive the C-Pulse[®] System with immediate therapy following implant and OMT while the Control group will continue on OMT. The subjects will not be allowed to cross-over from the assigned group (i.e. a control will not be allowed to receive a C-Pulse). If a treatment subject is explanted, it will be reported in the study analysis per the statistical methods section.

This study will include up to 40 centers in the US and potentially some Canadian centers. The study population will include 388 patients. All subjects who meet eligibility requirements and sign study consent will then be randomized following the baseline testing completion. The follow-up period will be for a minimum of 12 months to assess the safety and efficacy. To facilitate the analysis of the therapeutic effect, it is desired that the system be used all the time. The subject must limit disconnection to a minimal amount of time allowed for personal convenience such as hygiene. The Driver logs subject usage automatically and stores this usage into the system files.

Subjects will be followed for up to five years.

If a subject undergoes anesthesia for the purpose of C-Pulse implantation but does not receive a C-Pulse System, the subject will be followed for 30 days for safety or until they are discharged, whichever occurs first.

[figure not shown]

Figure 1. Study Design Flowchart

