In the event the subject becomes lost to follow-up, the investigational site should make two documented attempts to contact the subject. A Study Exit record must be completed and the subject will no longer be followed in the clinical study.

Data Collection Overview

A review of patient files is required to determine preliminary eligibility according to patient inclusion and exclusion criteria. Baseline data including functional tests must be collected no more than **30** days prior to randomization. Baseline imaging such as echo and CT scans must be collected no more than 90 days prior to randomization. See the data collection table for details.

Follow-up data will be collected at the time of implant, hospital discharge, at planned follow-ups (6 week, 3, 6, 12, 18-month and annually from the implant date thereafter up to 5 years). All serious adverse events will be collected throughout the study until closure.

All study subjects will follow the prescribed follow-up scheduled despite randomization. Day 0 for the treatment group will be the day of implant. Day 0 for the Control Group will be the day of randomization. Each group will continue with optimal medical therapy for the duration of the study, including all standard of care medications and treatments including transplant, VAD, etc. If the subjects are transplanted or placed on another device they will be censored from the primary endpoint analysis and study exited. Subjects implanted with the C-Pulse will be followed until device removal. If the PIL is explanted and not replaced, the subject will be followed for safety until removal of the entire system.

Data will be collected via electronic data capture (EDC) screens referred to as e-case report forms (eCRFs). Echocardiogram tapes and digital storage media must be documented in the patient medical record for source documentation.

Table 1, below outlines the data collection with the appropriate follow-up time windows.

Table 1. Follow-up Windows

Evaluation	Time Window
Pre-Implant Evaluation	No more than 30 days prior to implant
Randomization	Post Baseline Testing and Pre-Implant
Implant	Day 0 (Treatment Group) – Implant Day 0 (Control Group) – Randomization
Pre-Discharge	Within 36 hours prior to discharge
6 – week follow-up	Days 42 ± 7 Post-Implant
3 – month follow-up	Days 90 ± 14 Post-Implant
6 – month follow-up	Days 180 ± 30 Post-Implant
12 – month follow-up	Day 365 ± 30 Post-Implant
18 – month follow-up	Day 540 ± 30 Post-Implant

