The patient should not be discharged if any of the following issues are present:

- Unresolved system malfunction
- Back-up equipment is not available
- Unresolved adverse event that threatens patient safety
- Patient requires any treatment for disease, illness, mental or physical disability that cannot be provided outside the hospital

Post-Implant Follow-up Testing and Data Collection

Post-Implant Testing and Data Collection Summary

The complete reference list of post-implant testing and data collection that will be performed at each time point is included in Table 3.

Unscheduled Follow-up Visits

If subjects are seen between protocol-scheduled visits because of clinical symptoms requiring readmission, device reprogramming, etc. a follow-up form must be completed with all appropriate sections. In addition, all serious adverse events must be documented throughout the study.

System Modifications

Immediately contact Sunshine Heart clinical support team if a need is suspected for system modification (internal component or system replacement). In the event that the C-Pulse[®] System requires modification (e.g. Cuff or PIL) data collection must be recorded on the eCRFs along with an adverse event form. Modifications should be done only in communication with Sunshine Heart Inc. clinical personnel, unless the modification is a medical emergency, in which case, Sunshine Heart Inc. clinical personnel should be notified as soon as possible. In addition, the eCRF data collection must be completed documenting the removal of the existing device or component. The explanted C-Pulse[®] component(s) should be processed according to the Explant Handling Instructions and returned to Sunshine Heart Inc. or designee.

In the event of a system modification, including component removal, reposition or replacement of the entire C-Pulse[®] System, the follow-up schedule for the subject will remain unchanged (i.e. the subject should continue to be seen for follow-up and associated forms should be completed based on the original follow-up schedule). All serious adverse events should be reported and classified by the investigator. Additionally the CEC will provide further classification of adverse events.

Adverse Event Reporting

Overview

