Report all associated adverse events. Update the device tracking records with all products. If the device is not returned to Sunshine Heart Inc., justification must be provided in the log.

Subject Withdrawal and Study Exit

A Study Exit record shall be completed if subject is unable to or refuses to continue participation in the study. Notify the Sunshine Heart clinical support team as soon as possible upon learning of a subject withdrawal/study exit.

If the subject fails to comply with follow-up visits, the study center must make repeated attempts to contact the subject. Each attempt to contact the subject must be documented in the subject's records and in the database.

If the subject officially withdraws from the study, the investigator will document the reason for withdrawal and indicate any relationship of the withdrawal to the study or the device on the eCRF.

If a subject withdraws from the study at any time, there will be no penalty or loss of future medical care.

STATISTICAL METHODS AND DATA ANALYSIS

Analysis Population

All randomized subjects will be included in the evaluation of the primary efficacy objective. Subjects will not be allowed to cross-over. All subjects implanted with the C-Pulse System will be included in the evaluation of the primary safety objective. In the event a randomized subject does not receive the implant or does not receive the randomized therapy, the subject will be analyzed according to the randomized assignment for the primary analyses. Additional supporting analyses of the primary efficacy endpoint will be conducted (as treated and per-protocol) which exclude subjects who do not receive the randomized treatment or those with major protocol deviations. The defined analysis cohorts are:

- Intent to treat: All randomized subject irrespective of treatment actually received (primary efficacy analysis)
- As treated: All randomized subjects receiving treatment as randomized
- Per protocol: All randomized subjects without major protocol deviations

Primary Efficacy Endpoint

The primary efficacy endpoint is defined as freedom from worsening heart failure related hospitalization, LVAD implant, heart transplant, and death.

The primary efficacy endpoint includes all occurrences of worsening heart failure events and will be analyzed utilizing a multiple failure time analysis.

Hypotheses

H_0 : HR=1,

H_A : HR \neq 1,

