The primary safety endpoint is 12 month freedom from serious adverse events that are adjudicated definitely related to device, therapy or procedure and resulting in either surgical intervention or death. All serious adverse events that are adjudicated by CEC to be definitely related to device, therapy or procedure and result in either surgical intervention or death will be included in the analysis. Events will be reported by number of event and proportion of subjects with event along with the ninety-five percent binomial exact confidence limits. Only first event counts towards the endpoint for each subject.

The proportion of C-Pulse[®] subjects free from serious adverse events that are adjudicated definitely related to device, therapy or procedure and result in surgical intervention or death through 12 months following implant and will be compared to the performance goal (PG) of 0.60.

The hypotheses are:

$$H_0: \Pi \leq PG,$$

$$H_A: \Pi > PG,$$

where Π is the 12 month freedom from serious adverse events that are definitely related to device, therapy or procedure and resulting in either surgical intervention or death and PG is the performance goal. If the lower, two-sided, 95% confidence bound is greater than 0.6 the objective will be met.

Primary Safety Endpoint Sample Size

Sample size was estimated for a combined freedom from serious adverse events adjudicated definitely related to device, therapy or procedure resulting in surgical intervention (to repair, replace or remove the implanted device) or death. The minimum required sample size and total number of device related deaths and device related surgical intervention events was calculated under the following assumptions:

- Significance level = 0.05
- Power = 0.80
- 12 month freedom from serious adverse events definitely related to device, therapy or procedure resulting in either surgical intervention (to repair, replace or remove implanted device) or death event of 70%.
- Minimum follow-up of 12 months

Under the above assumptions a minimum of 182 subjects are required.

Justification for Primary Safety Endpoint Sample Size

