The poolability of the primary efficacy endpoint across clinical sites will be assessed using a covariate adjusted proportional hazards regression model including an interaction term for clinical site and treatment group. In the event statistical evidence of a difference in treatment effect by site is found, an analysis utilizing a random effects model with a random effect for site will be conducted.

Type I Error Control for Secondary Objectives

The secondary efficacy objectives will be tested in a hierarchical fashion in the order listed only in the event the primary efficacy objective is met, thereby preserving an overall Type I error rate of 5%.

Handling of Missing Data

For the primary efficacy analysis, subjects lost to follow-up or explanted will be censored at the date of the last assessment.

Additional analyses of the follow-up assessments of KCCQ, six minute walk and LVEF will be conducted to assess the impact of missing data at month 12. The Wilcoxon Sign-Rank test with the worst rank imputed for data missing due to death, LVAD transplant, heart transplant or explant (in order of time to outcome) will be used to assess treatment differences in the continuous parameters while including subjects who withdrew from randomized treatment prior to the 12 month assessment. Multiple imputation analyses will be conducted to assess the robustness of the study results against data missing due to losses to follow-up and study non-compliance or un-interpretable test results.

Impact of Covariates on the Potential Treatment Differences

Additional exploratory statistical analyses of the primary and secondary study results will be conducted to assess for impact of selected baseline and follow-up parameters on the observed treatment differences. This will involve the stratification of results by categorical parameters and covariate adjusted regression analyses for the assessment of interaction with randomization assignment. Of particular interest will be an assessment for any treatment differences in the efficacy or safety parameters by gender. Other baseline covariates of interest will include classification based on race/ethnicity, age at implant, INTERMACS profile, NYHA, etiology (ischemic/non-ischemic), CRT/ICD therapy, angina, arrhythmia, hyperlipidemia and diabetes and the continuous covariates of baseline six-minute walk, KCCQ and MLWHF.

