Due to the possible interaction of site infection leading to “Deep” infection or tissue swelling around the intrathoracic gas line and /or ascending aorta an infection procedure monitoring process is recommended. The following process is recommended to reduce risk of injury to the patient.

Infection Monitoring Process:

In the presence of clinical signs (pain, redness, discharge, loss of driveline fixation) and /or microbiological evidence (positive wound culture) of infection (intermittent or chronic) over a 3 month period despite treatment.

Decision Process:

Are there clinical signs or microbiological evidence of infection over a 3 month period despite treatment?

- No: Continue therapy
- Yes: Perform CT or PET scan
 - If scan is positive (i.e. shows evidence of DEEP infection or soft tissue swelling around the intrathoracic gas line and/or ascending aorta or presence of intrathoracic gas), then REMOVE PIL AND CUFF.
 - If scan is negative (i.e. shows no evidence of DEEP infection), REMOVE PIL only.
 - If at the time of surgery there is clinical evidence of DEEP infection (i.e. pus or fluid around the ‘Y’- connector, positive gram stain, and infected tissue) then REMOVE the CUFF also.
- If at the time of CT/PET scan or surgery there is no evidence of DEEP infection, then REPEAT SCAN at 3 months post-op and monitor for clinical signs of infection, if none found then REPEAT SCAN annually.
- NOTE: if wound culture is positive for MRSA, MSSA or Pseudomonas, monitor more frequently with FOLLOW-UP CT-SCAN at 3 months.

Aortic Tissue Sampling Guideline

In the event of a heart transplant, LVAD placement or patient death in the control group, it is requested that a single tissue sample of the ascending aorta should be collected for analysis.

In the event of a heart transplant, LVAD placement or patient death in the treatment group, it is recommended that the C-Pulse system be removed. To ensure evaluation of the system and patient interaction the following process provides guidance on removal of the C-Pulse implanted components at the time of explant, the observations to be recorded and for device return for analysis.

- If possible, return the devices intact and connected. In the event of device dissection, attempt to maintain the connections intact.
- For the Cuff, balloon integrity should be maintained unless histopathological analysis requires dissection.

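### The primary analysis is called intent-to-treat, yet it censors C-Pulse subjects at explant, which can happen in one arm only

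*Combined protocol and SAP*

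**What the plan says.** - **Analysis Population** defines the primary cohort as "Intent to treat: All randomized subject irrespective of treatment actually received (primary efficacy analysis" and keeps subjects who never receive the implant in their randomized arm.
- **Design** bars controls from receiving a C-Pulse and passes explants on: "If a treatment subject is explanted, it will be reported in the study analysis per the statistical methods section".
- **Handling of Missing Data** is where that pointer leads, and it holds the only explant rule for the primary endpoint: "For the primary efficacy analysis, subjects lost to follow-up or explanted will be censored at the date of the last assessment".
- **Data Collection Overview** limits what is observed: "Subjects implanted with the C-Pulse will be followed until device removal". For removal of the percutaneous lead (PIL) alone: "If the PIL is explanted and not replaced, the subject will be followed for safety until removal of the entire system".
- **System Modifications** says that after removal of a component, or replacement of the system, "the follow-up schedule for the subject will remain unchanged".
- **Appendix K, Infection Monitoring Process**, foresees whole-system removal after a positive scan ("then REMOVE PIL AND CUFF"). Appendix B reports explants in the feasibility study for weaning, transplant and LVAD.

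**The concern.** An intent-to-treat comparison needs outcomes to be counted after treatment stops, not only subjects to be kept in their assigned arm. Here a device subject leaves the analysis when the system is removed, and later heart failure hospitalizations, LVADs, transplants and deaths are not counted. A control has no equivalent exit.

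This is harmless only if removal is unrelated to prognosis and hazard does not change afterwards. The documents give reasons to doubt both. The Device Failure section says that symptoms may return when the device stops. The reasons for removal run from infection and deterioration to recovery. The plan itself ranks explant alongside death, LVAD and transplant for the walk, LVEF and KCCQ, but treats it as neutral for the primary endpoint. That is an inconsistency, not evidence of a higher hazard.

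At stake is the HR on which the efficacy claim rests. Outcomes not collected after explant may be impossible to recover later.

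**Working it through.** **1. Reproducing the plan's sample size.** Inputs from Primary Efficacy Endpoint Sample Size: control 6-month freedom 0.72, HR 0.70, two-sided 0.05, power 0.80, accrual 2.5 years, minimum follow-up 1 year, attrition 10% per year, 1:1.

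- Control hazard λ = −ln(0.72)/0.5 = 0.657 per year; device 0.70 × 0.657 = 0.460; attrition μ = −ln(0.9) = 0.105.
- Events (Schoenfeld): 4(1.960 + 0.842)²/(ln 0.70)² = 247.
- Event probability: λ/s × [1 − (e^(−s) − e^(−3.5s))/(2.5s)], with s = λ + μ. Control 0.682, device 0.566, mean 0.624.
- N = 247/0.624 ≈ 396, within about 2% of the planned 388. At 388, expected first events are 388 × 0.624 = 242 and power is 78–79%.
- The stated 265 events match 388 × 0.685, the expectation without attrition. This does not affect the present point.

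**2. How common explant could be.** No rate is given. The nearest figure is the safety planning value, 12-month freedom from related events "resulting in either surgical intervention (to repair, replace or remove implanted device) or death event of 70" percent, so 30% are assumed to have a definitely related repair, replacement, removal or death. If removals are a third, two thirds or all of these, explant by 12 months is 10, 20 or 30%. The last is the ceiling for such removals; recovery explants would be extra. Explant hazards are h = −ln(0.9), −ln(0.8) and −ln(0.7), that is 0.105, 0.223 and 0.357 per year.

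Expected number explanted under follow-up:
- first 12 months only: 194 × h/(h+μ) × [1 − e^(−(h+μ))];
- continuing at the same rate: the formula of step 1 with h in place of λ.

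**3. Effect on the HR when explant is unrelated to prognosis.** First-event Cox model, on-device HR 0.70, hazard back to the control level after removal. Ranges run from first-12-months-only to continuing removal.

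| Explanted by 12 months | 10% | 20% | 30% |
|---|---|---|---|
| Subjects explanted, of 194 | 18–36 | 37–67 | 55–94 |
| Device-arm follow-up cut off | 8–11% | 15–22% | 23–32% |
| HR, censored at explant | 0.70 | 0.70 | 0.70 |
| HR, everyone followed | 0.72 | 0.73–0.74 | 0.75–0.77 |
| Device first events uncounted | 9–12 | 18–24 | 28–35 |
| Power, everyone followed | 71–73% | 64–67% | 55–60% |
| Power, censored at explant | about 77% | about 75% | about 73% |

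Other post-explant hazards (continuing removal): at 1.5 times control, the HR with everyone followed is 0.75, 0.81 and 0.86. At half the on-device hazard, as after successful weaning, it is 0.67, 0.64 and 0.61, and power rises to about 85–97%.

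**4. Effect when explant is related to prognosis and the device does nothing (true HR 1).** Gamma frailty, variance 0.5–1, calibrated to 0.72 at 6 months. False benefit means z < −1.96 (nominal 2.5%).

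| Who is explanted | Censored HR at 10% | Censored HR at 30% | False benefit at 10%, 30% |
|---|---|---|---|
| Sicker, hazard proportional to frailty | 0.96–0.97 | 0.87–0.92 | 4–5%, about 8–16% |
| Sicker, link in half of subjects | 0.98–0.99 | 0.93–0.96 | about 3–4%, about 5–7% |
| Healthier, frailty rank reversed | 1.02–1.06 | 1.09–1.18 | below 2.5% |
| No link | 1.00 | 1.00 | nominal |

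With everyone followed, the null HR is 0.99–1.00 with 2–3% error. Lognormal frailty (SD 1) gives 0.96 and 0.89 if sicker subjects are removed, 1.05 and 1.13 if healthier.

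**5. All events.** The protocol does not name its multiple-failure-time model. An Andersen-Gill fit with robust variance, assuming 20% of events are terminal, gives 0.92–0.95 at 10% and 0.77–0.86 at 30% if sicker subjects are removed, and 1.05–1.07 and 1.14–1.23 if healthier. I treat this as sensitivity only.

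**6. Censoring date.** Nominal visits in days are 0, 42, 90, 180, 365, 540 and 730, then yearly, so gaps are 42, 48, 90, 185, 175, 190 and then 365. If the last assessment means the last scheduled visit, on-device events before removal can also be lost.

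**The case against.** - *The plan defines an ITT cohort, not an estimand, and states its censoring rule openly.* True as to wording. But the label then describes an analysis that ignores post-treatment outcomes in one arm, and Design offers no other rule for explants.
- *The large false-benefit figures are near worst case.* Correct. They need every planned safety event to be a whole-system removal and a full link to frailty, while the Appendix K trigger is infection. With half the link, false benefit at 30% falls to about 5–7%.
- *The power loss should be judged against the current rule, not a trial without explants.* Accepted; the table does so.
- *Adverse events are collected to closure, and the visit schedule survives system modification.* Collection does not help if the analysis excludes the events. The schedule rule covers component removal and system replacement, so the loss is mainly whole-system removal.
- *An explant would generate its own record, so a long gap before censoring is unlikely.* Reasonable. Naming the explant date would settle it.
- *Other analyses may cover this.* As-treated and per-protocol sets restore no follow-up. The worst-rank analysis concerns the walk, LVEF and KCCQ, and the imputation described beside it does not mention explant. The protocol defers method detail to a separate Statistical Analysis Plan, which may add something, but the primary rule is stated outright in the protocol.

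**Conclusion.** The point stands. As written, the primary HR compares device subjects up to explant with controls followed throughout, so it is closer to an on-device contrast than to the effect of assignment. I say closer because subjects never implanted stay in the device arm, and PIL-only removals may stay under observation.

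The direction is not established. Under the assumed 10–30% explant, the gap between the reported and the full intent-to-treat HR is about 0.02 to 0.07 if hazard returns to the control level, larger if it rises above that, and reversed if removals follow recovery. The rates, post-explant hazards and frailty links are assumptions. The contradiction between sections is not.

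Related passages that must be reconciled at the same time:
- Explanted is not defined (PIL only or whole system).
- Design ends follow-up of a failed implant at 30 days or discharge, while Data Collection Overview puts every subject on the full schedule.
- Data Collection Overview censors subjects at transplant or another device, although the endpoint definition counts LVAD and transplant as events. It may mean that the event counts and then ends follow-up, but it does not say so.

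**What to change.** 1. In Handling of Missing Data, remove explant as a reason for censoring. Censor only at withdrawal, loss to follow-up or the common cut-off.
2. Amend Data Collection Overview and Design so that every randomized subject is followed for primary-endpoint events to that cut-off, whatever happens to the device or the implant attempt, by records or telephone if needed.
3. State that LVAD and transplant count as events in both arms.
4. Keep censor-at-explant as a supportive on-device analysis, with explant defined and censoring at the explant date.
5. Make the Statistical Analysis Plan and the interim analysis follow the same rule, and state whether HR 0.70 is the intent-to-treat or the on-device effect.

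**Cost.** A protocol and SAP amendment, plus light follow-up of roughly 18–94 of 194 explanted subjects and any failed implants. Adverse events are already collected to closure and consent covers five years, so the added work is modest. If 0.70 is only the on-device effect and hazard returns to control, power at 388 is about 71–73, 64–67 and 55–60% at 10, 20 and 30% explant, against about 77, 75 and 73% under the present rule. For 80% power, first events would rise from 247 to 291, 347 or 460 at an intent-to-treat HR of 0.72, 0.74 or 0.77 (Schoenfeld formula above). If removals mostly follow recovery, power rises instead.
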